9.3 INTERIM ANALYSES

No interim analyses will be performed.

9.4 ADJUSTMENTS FOR MULTIPLICITY

The study involves multiple comparisons. Procedures will be used to control for the overall Type I error rate at the significance level of 0.05. The following ordered comparisons of blocking effect will be tested at the 0.05 level of significance:

1. Hydromorphone 6 mg vs Hydromorphone 0 mg for CAM2038 q1w 32 mg;
2. Hydromorphone 6 mg vs Hydromorphone 0 mg for CAM2038 q1w 24 mg;
3. Hydromorphone 18 mg vs Hydromorphone 0 mg for CAM2038 q1w 32 mg;
4. Hydromorphone 18 mg vs Hydromorphone 0 mg for CAM2038 q1w 24 mg;

Blockade effect cannot be claimed unless all preceding blocking effects, if any, are established.

9.5 PK/PD RELATIONSHIPS

The relationship between plasma BPN concentration and blockade of the subjective opioid effects of hydromorphone will be explored as appropriate.

9.6 POWER AND SAMPLE SIZE JUSTIFICATION

A sample size of 24 subjects will provide 90% power for the CAM2038 32 mg to demonstrate no significant difference in the mean E_{\max} score of the Drug Liking VAS comparing to 0 mg hydromorphone at a two-sided 0.05 significance level with a non-significant difference cutoff at ≤ 11 points. In the sample size calculation it was assumed that the true difference was less than or equal to 1.5 and the standard deviation was 9.8.

Additional 24 subjects will be enrolled to CAM2038 24 mg group. This sample size will provide approximately 83% power for the CAM2038 24 mg to demonstrate no significant difference in the mean E_{\max} score of the Drug Liking VAS comparing to 0 mg hydromorphone at a two-sided 0.05 significance level with a non-significant difference cutoff at ≤ 11 points. In the sample size calculation it was assumed that the true difference was less than or equal to 2.5 and the standard deviation was 9.8.

The plan will be to enroll a sufficient number of subjects to ensure that approximately 48 subjects complete the study (24 subjects per treatment group) by over-enrollment as needed.

10.0 SUMMARIES OF PHARMACOKINETIC ANALYSIS

Pharmacokinetic endpoints include:

The following pharmacokinetic parameters will be estimated for BPN and norbuprenorphine:

- C_{\max} (maximum plasma concentration)
- C_{trough} (plasma concentration level 7 days after the latest injection)
- C_{av} (average plasma concentration during a dosing interval)

C_{av} will be calculated as (AUC_{0-168h}/τ) , where AUC_{0-168h} is the area under the plasma concentration-time curve (AUC) between time 0 and 168 hours after latest injection and τ the dosing interval (168 hours). AUC_{0-168h} will be calculated using the linear trapezoidal method up to C_{\max} and the logarithmic trapezoidal method for the remainder of the curve up to 168 hours after latest injection.

The PK parameters will be calculated using Phoenix WinNonlin Version 6.3 (or higher). The actual sampling times relative to dosing rather than the nominal times will be used in the calculations. BPN and norbuprenorphine plasma concentrations over time as well as all above PK parameters will be summarized by dose (32 mg and 24 mg) separately.

11.0 SUMMARIES OF MEASURES OF SAFETY

Safety analyses will be performed for the safety population. Safety evaluations will be based on the incidence, intensity, and type of adverse events, as well as on clinically significant changes in the subject's physical examination, vital signs, and clinical laboratory results, Injection site examination and wound care. Safety variables will be tabulated and presented by study drug actually received.

Because there is no pre-specified safety outcome defined in terms of AEs, clinically relevant laboratory parameters, or vital signs, any formal comparisons between the treatment arms with respect to specific safety parameters will be post-hoc.

11.1 EXTENT OF EXPOSURE

Summary statistics (number and percentage) of weeks of exposure to study drug (frequency of number of injections received) will be tabulated by treatment group.

11.2 ADVERSE EVENTS

Each AE and SAE term recorded on the case report forms (CRFs) by primary system organ class (SOC) and will be mapped to a preferred term using the MedDRA dictionary. The investigator will assess AE severity and relationship to the study treatment.

A treatment emergent adverse event (TEAE) is defined as any AE with an onset date on or after date of randomization, or any ongoing event on the date of first dose that worsens in severity after date of randomization. Only TEAEs with an onset date prior to date of last dose + 30 days will be tabulated in summary tables. For the purpose calculating treatment emergence and inclusion in summary tables, incomplete onset dates will be imputed as detailed in Appendix B.

AEs will be summarized by the number and percent of subjects in each primary SOC and preferred term. Patients will be counted only once for each primary SOC and each preferred term. Summary tables of AEs by primary SOC, preferred term and intensity will be provided. If a subject has more than one AE coded to the same preferred term, the subject will be counted only once for that preferred term by using the event with the highest intensity. Similarly, if a subject has more than one AE within a primary SOC category, the subject will be counted only once in that SOC category by using the event with the highest intensity. AEs by primary SOC, preferred term and relationship to study drug will be provided as well. If a subject has more than one AE coded to the same preferred term, the subject will be counted only once for that preferred term by using the most related event. Similarly, if a subject has more than one AE within a primary SOC category, the subject will be counted only once in that primary SOC category by using the most related event. In addition, serious adverse events (SAE) by primary SOC and preferred term will be provided. Deaths and SAEs will be summarized similarly to AEs. All adverse event tables will also include the total number of events, counting multiple events per patient.

AEs will be presented by treatment group (CAM2038 q1w of 24 mg or 32 mg and by hydromorphone treatment groups i.e., 0 mg 6 mg or 18 mg – during qualification period- and CAMP2038 relevant dose/hydromorphone relevant dose – on the days of hydromorphone challenges) and overall. An AE will

be attributed to a hydromorphone dose, if the AE occurred within one hour of the dosing (if the time of the AE is missing, the AE will be attributed to CAM2038). Summaries of these AE subsets will be presented for the following categories:

- Study drug related
- Intensity
- Relationship to injection (Suspected or Not Suspected)
- Suspected to be study drug related by intensity
- Serious
- AEs which led to discontinuation
- SAEs which led to discontinuation
- AEs occurring in 5% or greater of any treatment group (by preferred term)

In the AE summary, preferred terms within each SOC will appear in alphabetical order.

Frequencies for deaths and hospitalizations will also be summarized by treatment group and overall.

Other safety analyses will be performed as appropriate

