### Name of Investigational Product:

CAM2038 q1w (buprenorphine FluidCrystal® once-weekly subcutaneous (SC) injection depot)

Name of Active Ingredient: buprenorphine (BPN)

Following the Qualification/Baseline Hydromorphone Challenge Session, eligible subjects will be randomized in a 1:1 ratio to 1 of 2 groups, stratified by gender, to receive CAM2038 q1w at doses of 24 mg or 32 mg. Subjects will receive once weekly SC injections of CAM2038 q1w for 2 weeks (injections on Day 0 and Day 7) and will remain inpatient in the CRU for up to 25 days (including Qualification Phase), during which time 4 Hydromorphone Challenge Sessions (3 consecutive days each) will be conducted on Days 1 to 3, Days 4 to 6, Days 8 to 10, and Days 11 to 13, respectively. Safety and pharmacodynamic assessments will be performed on each day of the Hydromorphone Challenge Sessions at multiple timepoints beginning at pre-dose until approximately 5 hours post-dose. Plasma samples to quantify BPN and obtain norbuprenorphine levels will also be collected approximately 60 minutes prior to hydromorphone dosing on each day of the Hydromorphone Challenge Sessions.

Subjects will be discharged on Day 14 and a follow-up phone interview will be conducted on approximately Day 21.

The degree of hydromorphone dose tolerability will be determined based on the site-specific study Investigator's review of the subject's oximetry data, vital signs, behavior, and physical demeanor.

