Randomization will be used to avoid bias in the assignment of treatment for all the Hydromorphone Challenge Sessions and in the assignment of subjects to the 24 mg or 32 mg CAM2038 q1w dose groups during the Treatment Phase. Prior to the Qualification/Baseline Hydromorphone Challenge Session, subjects will be randomized to 1 of 6 challenge sequences, according to two 3 x 3 William squares (ABC, ACB, BAC, BCA, CAB, CBA), and will receive one dose of hydromorphone daily over 3 consecutive days, including 2 doses of hydromorphone and 1 dose of placebo. This approach has previously been shown to be sensitive to identifying dose-related agonist effects, while ensuring that both subjects and staff remain blinded to the dose of hydromorphone or placebo being administered, thereby reducing the risk of potential expectancy effects. As an additional precaution, subjects will be housed in inpatient research units for the duration of the study both for safety monitoring and to ensure that the subjects do not use other illicit opioids while enrolled in the study, as this may affect the Hydromorphone Challenge Session results.

Randomization increases the likelihood that known and unknown subject attributes (e.g., demographics and baseline characteristics) will be evenly balanced across dose groups and enhance the validity of statistical comparisons across dose groups. It was not possible to include a placebo control group (CAM2038 SC Placebo injection) in the current study because the enrolled population will be physically dependent on opioids and would go into opioid withdrawal with placebo administration. Therefore, this study includes a Qualification/Baseline Hydromorphone Challenge Session to establish the frequency and magnitude of changes in clinical endpoints that may occur in the absence of CAM2038 q1w.

Version: 2.0, 17NOV2015 Page 43 of 99

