#### 12.3.4.1. Adverse Events

Adverse events will be coded by system organ class (SOC) and preferred term using the Medical Dictionary for Regulatory Activities (MedDRA) reporting system. Treatment-emergent AEs are defined as any of the following:

- Non-serious AEs with onset on the date of first dose of treatment with the study drug through discharge or Early Termination, whichever occurs first;
- Serious AEs with onset on the date of first dose of treatment with the study drug through 30 days after discharge or Early Termination, whichever occurs first;
- AEs that start before the start of treatment but increase in severity or relationship at the time of or following the start of treatment through discharge or Early Termination, whichever occurs first.

The number and percentage of subjects with TEAEs will be displayed for each treatment group. During the Qualification Phase subjects TEAEs will be displayed by IR morphine 30 mg

Version: 2.0, 17NOV2015 Page 72 of 99

treatment or by hydromorphone treatment groups i.e., 0 mg 6 mg or 18 mg - on the days of hydromorphone challenges. During the Treatment Phase, TEAEs will be displayed by CAM2038 q1w relevant dose and hydromorphone relevant dose i.e., 0 mg 6 mg or 18 mg - on the days of hydromorphone challenges. TEAEs will be displayed by SOC and preferred term. Additionally, TEAEs will be tabulated for each treatment group by severity and by relationship to the study drug. A listing of SAEs will be provided if applicable.

If an AE is considered to be caused by a drug, the Investigator will note which drug caused the AE.

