Following the 3-day Qualification/Baseline Hydromorphone Challenge Session (Days -3 to -1), eligible subjects will be randomized in a 1:1 ratio to one of 2 groups to receive CAM2038 q1w at doses of 24 mg or 32 mg, stratified by gender. Subjects will receive two, once weekly injections of CAM2038 q1w, 7 days apart, (injections on Day 0 and Day 7) and will remain inpatient in the CRU for a total of approximately 3 weeks, during which time, 1 qualification/baseline Hydromorphone Challenge session will occur prior to CAM2038 administration then 4 Hydromorphone Challenge Sessions (3 consecutive days each with dose randomized) will be conducted on Days 1 to 3, Day 4 to 6, Days 8 to 10, and Days 11 to 13 after the first CAM2038 administration. Each Hydromorphone Challenge Session will consist of 3 doses of hydromorphone 10 mg/mL IM injections (doses of 0 mg [placebo], 6 mg and 18 mg) administered on 3 consecutive days in randomized order. Eligible subjects will be randomized in a 1:1:1:1:1:1 ratio to 1 of 6 treatment sequences according to two 3×3 William squares. The following treatment sequences will be used: ABC, ACB, BAC, BCA, CAB, and CBA, where A, B, and C are IM hydromorphone doses, 0 mg (placebo), 6 mg, and 18 mg, respectively. The doses, 0 mg (placebo), 6 mg or 18 mg, will be administered once daily during the hydromorphone challenge sessions. Safety assessments will be conducted immediately following each dose of hydromorphone administered in each Challenge Session and scheduled pharmacodynamic evaluations will occur over approximately 5 hours post dose. Plasma BPN and norbuprenorphine (NorBPN) levels will also be obtained approximately 60 minutes prior to hydromorphone dosing (predose) on each day of the Hydromorphone Challenge Sessions.

Subjects will be discharged on Day 14 and a follow-up phone interview will be conducted on Day 21. The degree of hydromorphone dose tolerability will be determined based on the site-specific study Investigator's review of the subject's oximetry data, vital signs, behavior, and physical demeanor.

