TABLE 14.2.11.1b	Summary of Change from Baseline in Objective Opioid Withdrawal Scale (OOWS) for CAM2038 24 mg (Completer Population)
TABLE 14.2.11.2a	Summary of Change from Baseline in Objective Opioid Withdrawal Scale (OOWS) for CAM2038 32 mg (ITT Population)
TABLE 14.2.11.2b	Summary of Change from Baseline in Objective Opioid Withdrawal Scale (OOWS) for CAM2038 24 mg (ITT Population)
TABLE 14.2.12.1a	Summary of BPN and norpuprenorphine Concentrations for CAM2038 32 mg (Completer Population)
TABLE 14.2.12.1b	Summary of BPN and norpuprenorphine Concentrations for CAM2038 24 mg (Completer Population)
TABLE 14.2.12.2a	Summary of PK Parameters for CAM2038 32 mg (Completer Population)

TABLE 14.2.12.2b	Summary of PK Parameters for CAM2038 24 mg (Completer Population)
TABLE 14.3.1	Summary of CAM2038 Exposure (Safety Population)
TABLE 14.3.2	Summary of All Adverse Events by System Organ Class, Preferred Term, and Relationship to Hydromorphone During Qualification Period (Safety Population)
TABLE 14.3.3.1	Summary of All Adverse Events by System Organ Class, Preferred Term, and Intensity for CAM2038 Doses and Overall (Safety Population)
TABLE 14.3.3.1.2	Summary of All Adverse Events by System Organ Class, Preferred Term, and Intensity for Hydromorphone and CAM2038 24 mg (Safety Population)
TABLE 14.3.3.1.3	Summary of All Adverse Events by System Organ Class, Preferred Term, and Intensity for Hydromorphone and CAM2038 32 mg (Safety Population)
TABLE 14.3.4.1.1	Summary of All Adverse Events by System Organ Class, Preferred Term, and Relationship to Study Drug for CAM2038 Doses and Overall (Safety Population)
TABLE 14.3.4.1.2	Summary of All Adverse Events by System Organ Class, Preferred Term, and Relationship to Study Drug for Hydromorphone and CAM2038 24 mg (Safety Population)
TABLE 14.3.4.1.3	Summary of All Adverse Events by System Organ Class, Preferred Term, and Relationship to Study Drug for Hydromorphone and CAM2038 32 mg (Safety Population)
TABLE 14.3.5	Summary of All Suspected to Be Drug Related Adverse Events by System Organ Class and Preferred Term for CAM2038 Doses and Overall (Safety Population)
TABLE 14.3.6	Summary of Most Common (at least 5%) Adverse Events by System Organ Class and Preferred Term for CAM2038 Doses and Overall (Safety Population)
TABLE 14.3.7	Summary of All Serious Adverse Events by System Organ Class and Preferred Term for CAM2038 Doses and Overall (Safety Population)

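### SAP 11.2 does not say which of two randomizations starts the treatment-emergent window, so Qualification events may drop out of their planned table or become treatment-emergent before any CAM2038; the end of the window also differs from the protocol

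*SAP*

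**What the plan says.** **Start of the window.** SAP 11.2 opens its definition of a treatment-emergent event (TEAE) with "any AE with an onset date on or after date of randomization". A second limb deals with events already present: "any ongoing event on the date of first dose that worsens in severity after date of randomization". That limb uses two different anchors in one clause. Protocol 12.3.4.1 uses first dose instead: "Non-serious AEs with onset on the date of first dose of treatment with the study drug through discharge or Early Termination, whichever occurs first". For serious events the start is the same, with a later end.

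**Two randomizations.** Protocol 7.2: "Prior to the Qualification/Baseline Hydromorphone Challenge Session, subjects will be randomized to 1 of 6 challenge sequences". Protocol synopsis, Methodology: "Following the Qualification/Baseline Hydromorphone Challenge Session, eligible subjects will be randomized in a 1:1 ratio to 1 of 2 groups". SAP 4.3 agrees on the second, which it places after the Qualification challenge: "eligible subjects will be randomized in a 1:1 ratio to one of 2 groups to receive CAM2038 q1w". Neither document gives the calendar day of either randomization.

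**What is tabulated.** SAP 11.2: "Only TEAEs with an onset date prior to date of last dose + 30 days will be tabulated in summary tables". The same section plans a Qualification display by hydromorphone dose, and SAP Appendix A lists Table 14.3.2, whose title ends "Relationship to Hydromorphone During Qualification Period (Safety Population". Protocol 12.3.4.1 displays Qualification TEAEs by IR morphine or by hydromorphone dose. The SAP lists no IR morphine display.

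**Attribution and imputation.** SAP 11.2 assigns an event to hydromorphone if it occurs within one hour of the dose, and to CAM2038 if its time is missing. Appendix B sets a completely missing onset date to the date of randomization. Elsewhere in the same algorithm it uses first dose.

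**The concern.** The two randomizations lie on either side of the Qualification challenge, which is the only period in which subjects receive 6 mg and 18 mg hydromorphone without CAM2038. Protocol 7.2 explains that a placebo depot arm was not possible, so this period is the trial's only reference for events in the absence of CAM2038.

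An unspecified randomization date therefore decides whether those events are treatment-emergent at all. If they are, it is also unclear which table they belong in. Two competent programmers could follow the SAP and produce different safety tables. The safety of CAM2038 given with hydromorphone is a stated secondary objective, and these tables are the main evidence for it.

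**Working it through.** No figure in the plan depends on this definition, so there is none to reproduce. The check counts days under each reading and then follows the events through the SAP's own rules.

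**Step 1. Qualification days that count as treatment-emergent.** Input: the longest Qualification stay, Day -10 to Day -1, which is 10 days (Protocol 7.1.2.1). For an anchor on Day a (a ≤ 0), the number of Qualification days on or after it is 0 − a. The randomization days are assumed ranges, because the documents only say before or after the challenge.

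| Anchor | Assumed day | Qualification days counted | Challenge days among them |
|---|---|---|---|
| Sequence randomization | -4 | 0 − (-4) = 4 | 3 |
| Sequence randomization | -3 | 0 − (-3) = 3 | 3 |
| CAM2038 randomization | -1 | 0 − (-1) = 1 | 1 |
| CAM2038 randomization | 0 | 0 | 0 |
| Protocol first dose, if that means IR morphine | -10 | 0 − (-10) = 10 | 3 |

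**Step 2. Follow the events through SAP 11.2.**

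- *CAM2038 anchor.* With tables limited to TEAEs, Table 14.3.2 can hold Day -1 events only (randomization dated Day -1) or nothing (dated Day 0).
- *Sequence anchor.* Events on Days -3 to -1 are TEAEs although no CAM2038 has been given. Tables 14.3.3.1 and 14.3.4.1.1 (all adverse events by CAM2038 dose) carry no restriction to a phase. An event with no recorded time goes to CAM2038, with no exception before Day 0. An event timed later than one hour after hydromorphone has no stated attribution in Qualification.
- *Either anchor.* IR morphine stabilization events that precede sequence randomization are not TEAEs, although Protocol 12.3.4.1 displays them.
- *Missing onset date.* Imputing it to randomization makes the event a TEAE every time, whichever randomization is meant.

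**Step 3. End of the window.** Inputs: discharge Day 14, last CAM2038 dose Day 7, last hydromorphone dose Day 13, follow-up call about Day 21. Protocol 10.4.1.1 collects AEs until 14 days after follow-up: 21 + 14 = Day 35.

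- Protocol, non-serious: last day 14. Protocol, serious: 14 + 30 = Day 44.
- SAP, last dose read as CAM2038: onset must be before Day 7 + 30 = 37, so the last day is 36.
- SAP, last dose read as hydromorphone: onset must be before Day 13 + 30 = 43, so the last day is 42.

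| Class | Protocol ends | SAP ends (Day 7 anchor) | Days that differ |
|---|---|---|---|
| Non-serious | 14 | 36 | 15 to 36: 36 − 14 = 22 |
| Non-serious, within AE collection | 14 | 35 | 15 to 35: 35 − 14 = 21 |
| Serious | 44 | 36 | 37 to 44: 44 − 36 = 8 |

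With the Day 13 anchor the serious gap is 44 − 42 = 2 days. The non-serious gap within AE collection stays at 21, because collection ends before either SAP limit.

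**The case against.** The best case for the plan has four parts.

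- **The SAP hints at its meaning.** SAP 4.2 describes the CAM2038 allocation first and places the sequences within the dose groups, so randomization without a qualifier probably means CAM2038. This makes one reading likelier. It does not state it, and the likelier reading is the one that empties or nearly empties Table 14.3.2.
- **Other rules keep the phases apart.** SAP 11.0 presents safety data by the drug a subject really received, and SAP 11.2 shows Qualification events by hydromorphone dose. A reader might infer that the sequence anchor turns every Qualification event into a CAM2038 event. The documents do not support that: these rules allow such events to be shown under hydromorphone only. Misallocation is possible, most directly through the missing-time default, but not forced.
- **A specific plan can override a general filter.** A reader might also infer that the CAM2038 anchor must leave the Qualification table empty. That holds only if randomization is dated Day 0 and the TEAE-only sentence governs a table titled as covering all adverse events. The SAP does not say which of the two prevails.
- **The SAP may depart from the protocol, and safety is descriptive.** Protocol section 12 allows the methods to be revised, and Protocol 12.3.4 plans no formal safety comparison. The protocol's first dose is itself unclear, since Protocol 9.2 lists IR morphine, hydromorphone and CAM2038 as study treatments. So no efficacy claim is at risk, and the protocol wording cannot simply be copied across. The need for a single, stated rule stands.

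**Conclusion.** The point holds as an undefined anchor with consequences for the safety tables, not as a choice between two certain errors. Under the CAM2038 date, between 0 and 1 of the 10 Qualification days can reach Table 14.3.2. Under the sequence date, all three challenge days are treatment-emergent before any CAM2038, with nothing explicit to keep them out of the CAM2038 tables. Neither reading captures stabilization events that precede sequence randomization. The end windows conflict by 22 days for non-serious events (about 21 of them within AE collection) and 8 days for serious events.

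These figures rest on three assumptions: sequence randomization on Day -4 or -3, CAM2038 randomization on Day -1 or 0, and last dose meaning CAM2038 on Day 7. The serious gap matters less in practice than its length suggests, because it lies after about Day 35. From then on, Protocol 10.4.1.2.1 asks for 24-hour reporting only of serious events considered possibly related. The correction should be made before database lock; it affects descriptive safety output only.

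**What to change.** 1. **Qualification AEs:** onset from the first IR morphine dose until before the first CAM2038 injection. Show them by IR morphine or by hydromorphone dose, and keep Table 14.3.2 for the challenge days, since its title concerns relationship to hydromorphone. State that the TEAE-only sentence does not exclude this set.
2. **Treatment TEAEs:** onset or worsening at or after the first CAM2038 injection. Add a date-level rule for Day 0 events with no recorded time, for example counting them as Treatment TEAEs. Protocol 10.4.1.1 lists onset date but not onset time among the AE items, so the rule will be needed.
3. **End of window:** state one end day, and which drug last dose refers to, identically in SAP 11.2 and Protocol 12.3.4.1. For non-serious events, a day beyond about Day 35 would run past AE collection.
4. **Missing-time default:** limit attribution to CAM2038 to events on or after Day 0.
5. **Appendix B:** replace the mixed randomization and first-dose anchors with the same first-dose anchors.

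The cost is wording in both documents, one derived phase flag, and a display for IR morphine events that the SAP does not now list. Day 0 events without a time may be classified less precisely. No new data are needed.

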#### 7.1.4. Hydromorphone Challenge Sessions

Each Hydromorphone Challenge Session in the Qualification Phase and Treatment Phase will consist of the injection of 3 doses of IM hydromorphone 10 mg/mL (0 mg [placebo], 6 mg and 18 mg) administered once daily over 3 consecutive days in randomized order. Subjects will be randomized in a 1:1:1:1:1 ratio to 1 of 6 treatment sequences according to two 3 × 3 William squares. The following treatment sequences will be used: ABC, ACB, BAC, BCA, CAB, and CBA, where A, B, and C are IM Hydromorphone Challenge Sessions with 0 mg (placebo), 6 mg, and 18 mg, respectively. The volume of the 0 mg and 6 mg doses of IM hydromorphone will be the same as the volume of the 18 mg hydromorphone dose. Safety and pharmacodynamic assessments will be performed immediately following each dose of hydromorphone administered on each day of the Hydromorphone Challenge Session for a maximum 5 hours after Hydromorphone Challenge Session. Plasma BPN and norbuprenorphine levels will also be obtained approximately 60 minutes prior to hydromorphone dosing on each day of the Hydromorphone Challenge Sessions. After each dose of hydromorphone, subject's oxygen saturation, respiratory rate, and overall safety profile will be reviewed by the research/nursing staff (as described in Section 7.1.2.1) to determine whether it is safe to proceed with administration of the next dose of hydromorphone.

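### Adverse events by hydromorphone dose are reported as percent of subjects with no count of administrations, so Qualification (one of each dose) and Treatment (up to four) are not on the same exposure basis

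*SAP*

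**What the plan says.** SAP 11.2 sets the summary statistic: "AEs will be summarized by the number and percent of subjects in each primary SOC and preferred term". The counting rule is "Patients will be counted only once for each primary SOC and each preferred term". It also promises event counts: "All adverse event tables will also include the total number of events, counting multiple events per patient".

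These summaries are broken down by hydromorphone dose in both phases (Protocol 12.3.4.1, SAP 11.2). In SAP Appendix A, Table 14.3.2 covers Qualification. Tables 14.3.3.1.2, 14.3.3.1.3, 14.3.4.1.2 and 14.3.4.1.3 cover hydromorphone under CAM2038 24 mg and 32 mg. No Treatment table title shows a split by challenge session. An event is attributed to a hydromorphone dose if it occurs within one hour of that dose. An event with no recorded time goes to CAM2038.

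On the schedule, SAP 4.3 says "1 qualification/baseline Hydromorphone Challenge session will occur prior to CAM2038 administration then 4 Hydromorphone Challenge Sessions", and Protocol 7.1.4 says "Each Hydromorphone Challenge Session in the Qualification Phase and Treatment Phase will consist of the injection of 3 doses of IM hydromorphone". Exposure is tabulated only for the depot: SAP 11.1 counts weeks and injections by treatment group, and Table 14.3.1 is titled as CAM2038 exposure. Nothing states how many hydromorphone administrations lie behind each column.

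Protocol 7.2 explains that a placebo depot was not possible and gives the purpose of the Qualification session as "to establish the frequency and magnitude of changes in clinical endpoints that may occur in the absence of CAM2038 q1w".

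**The concern.** The denominator is subjects, but an event can enter a hydromorphone column only in the hour after an injection of that dose. A subject has one such hour per dose at Qualification and up to four in Treatment. A subject who leaves early has fewer Treatment hours but counts fully in the denominator. The event totals do not repair this, because they also grow with the number of injections and are shown with no injection count beside them.

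Safety and tolerability of CAM2038 given together with hydromorphone is a secondary objective. Anyone asking whether the depot changes the tolerability of hydromorphone has only the Qualification table to compare with. Part of any difference seen there would come from the schedule alone, and the planned tables give no way to separate it out.

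**Working it through.** **Exposure.** Table 4 of the protocol (footnotes to the schedule) lists the challenge days: 3 at Qualification (Days -3 to -1) and 12 in Treatment (Days 1-6 and 8-13). Each session gives each of three doses once. Administrations of each dose per subject are therefore 3/3 = 1 and 12/3 = 4, which agrees with the one and four sessions in SAP 4.3. The ratio is 4:1 for a subject who completes.

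**Assumptions.** The documents give no adverse event rate. I assume a per-administration risk p that is the same with and without CAM2038 (range 2% to 30%) and an ICC of events across a subject's administrations (range 0 to 0.7).

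**Percent of subjects.** At Qualification it is p.

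- Treatment, independent administrations: 1 - (1 - p)^4. For p = 10%: 1 - 0.9^4 = 34.4%.
- Treatment, correlated administrations (beta-binomial): with a = p(1 - ICC)/ICC and b = (1 - p)(1 - ICC)/ICC, it is 1 minus the product of (b + i)/(a + b + i) for i = 0 to 3. For p = 10% and ICC 0.5, a = 0.1 and b = 0.9, so 1 - (0.900 × 0.950 × 0.967 × 0.975) = 19.4%.

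Percent of subjects in Treatment, with its ratio to Qualification in brackets:

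| p (Qualification) | ICC 0 | ICC 0.3 | ICC 0.5 | ICC 0.7 |
|---|---|---|---|---|
| 2% | 7.8% (3.88) | 5.2% (2.62) | 4.1% (2.05) | 3.2% (1.59) |
| 5% | 18.5% (3.71) | 12.7% (2.55) | 10.1% (2.01) | 7.8% (1.57) |
| 10% | 34.4% (3.44) | 24.3% (2.43) | 19.4% (1.94) | 15.3% (1.53) |
| 20% | 59.0% (2.95) | 44.0% (2.20) | 36.2% (1.81) | 29.3% (1.46) |
| 30% | 76.0% (2.53) | 59.7% (1.99) | 50.5% (1.68) | 41.9% (1.40) |

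The ratio runs from 1.4 to 3.9. It nears 4 only for rare, independent events (3.94 at p = 1%, ICC 0). It nears 1 when the same subjects react each time (1.13 to 1.18 at ICC 0.9). In a group of 24 completers, p = 10% with independence means 24 × 0.10 = 2.4 subjects expected at Qualification and 24 × 0.344 = 8.3 in Treatment. Event totals have an expected ratio of 4 whatever the correlation.

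**A true reduction.** Suppose CAM2038 halves the per-administration risk from 20% to 10%. Qualification shows 20%. Treatment shows 34.4% at ICC 0, 24.3% at ICC 0.3, 19.4% at ICC 0.5 and 15.3% at ICC 0.7. The two phases show the same percentage at an ICC of about 0.47, so the direction reverses only below that value.

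**After the fix.** The percent of administrations with an attributed event has expectation p in both phases, a ratio of 1.0, whatever the ICC.

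**The case against.** The strongest objection is that the plan never makes this comparison. Protocol 12.3.4 excludes formal testing of safety endpoints, and SAP 11.0 treats formal safety comparisons between arms as post hoc. The Qualification and Treatment figures sit in separate tables, mostly with different breakdowns. The objective concerns safety during co-administration. The contrast that serves it, 6 and 18 mg against 0 mg within a CAM2038 group, has four scheduled administrations in every column. Protocol 7.2 speaks of clinical endpoints and does not mention adverse events. A reader who knows the fixed schedule can also divide the event totals by one and four.

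Most of this stands. A reader might infer that Protocol 7.2 designates Qualification as the adverse event comparator; the text does not go that far. Within-phase dose comparisons are sound apart from early leavers. What remains is that descriptive displays are all the safety analysis the plan offers, and Qualification is the only place where hydromorphone is given without the depot. Readers have good reason to set the tables side by side. Dividing by one and four is inexact for early leavers, and it cannot convert percent of subjects into a per-administration figure without knowing the correlation.

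Equal exposure would not make the phases fully comparable. Entry to Treatment requires tolerating both active doses, subjects take IR morphine during Qualification, and untimed events are assigned to CAM2038. These limit the cross-phase reading but are not reasons to leave the exposure difference in it.

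**Conclusion.** The point holds as a shortcoming of presentation in descriptive safety tables. Percentages and event totals by hydromorphone dose rest on one administration at Qualification and up to four in Treatment, and the planned tables do not show this. With an unchanged per-administration risk, percent of subjects would be about 1.4 to 3.9 times higher in Treatment over p = 2% to 30% and ICC 0 to 0.7. Both ranges are assumptions.

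Two stronger readings are not supported. One is that the tables would show a fourfold excess; that is the limit for rare, independent events, and the ratio falls towards 1 as correlation rises. The other is that a real reduction would always look like an increase; for a halving from 20% to 10% this is so only if the ICC is below about 0.47. The primary analysis and the blockade claims are unaffected.

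**What to change.** In SAP 11.2 and Tables 14.3.2, 14.3.3.1.2, 14.3.3.1.3, 14.3.4.1.2 and 14.3.4.1.3, add for each hydromorphone dose:

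- the number of administrations actually given;
- the number and percent of those administrations with at least one adverse event attributed under the SAP's existing one-hour rule.

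The one-hour rule should define the numerator. Counting whole challenge days would bring in events that the SAP does not attribute to hydromorphone.

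Keep number and percent of subjects, with a footnote that these are not comparable between Qualification (one administration) and Treatment (up to four). Add a note that selection on tolerability, background IR morphine at Qualification and the missing-time rule still limit any comparison across phases.

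The cost is SAP wording plus one extra denominator and column in five tables. Study staff give every dose (Protocol 9.2.2 and 9.8), so dosing records should supply the counts and no new data are needed.
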